7.3. Safety reporting flow chart

[figure not shown]
Non-serious AE reporting responsibilities:

Investigational site
(completion of CRF) 

[figure not shown]
Data management department of
CRO and MedSIR (review,
evaluation, and processing of
safety data):
Quarterly lists of non-serious AEs

CRO/MedSIR will provide quarterly
lists of non-serious AEs for Bayer

AESI and SAE reporting responsibilities (as defined in the protocol):

Radium-223 treatment DSUR [DSUR form: Non-commercial Sponsor (MedSIR)]

n, and processing of safety information):
Drafting DSUR

Note: Bayer will send MedSIR an executive summary of Bayern's DSUR, at the request of MedSIR. MedSIR may cross reference Bayern's executive summary of DSUR.

Bayer (review, evaluation, and processing of safety data from sources other than those used in this clinical trial): Latest version of IB and IB updates, medical alert letters, and any new data that could modify or complement known data on radium-223, especially any new AEs and data related to radium-223 tolerance that may indicate a risk to patients:

MedSIR: ASAP

Managing safety crisis and safety-related requests from Health Authorities or for publications:

In the event of a safety crisis, e.g. cases where safety issues will potentially impact indication(s) or the conduct of the study that may give rise to changes in labeling or regulatory actions that limit or restrict the way in which radium-223 is used or in cases where the media is involved, the party (MedSIR) where crisis originated will contact the other party as soon as possible. Bayer will have final say and control over aspects related to the management of the safety crisis regarding.

MedSIR will not reply to any request related to the safety of radium-223 that it receives from the Health Authorities, the media or other sources (publications). Instead, it will direct requests to Bayern in accordance with and communicating the deadlines regarding necessary replies.

8. STATISTICAL CONSIDERATIONS AND STATISTICAL ANALYSIS PLAN

8.1. *Determination of sample size*

A total of 52 patients will be enrolled into this trial. We expect to include 13 AR-V7-positive and 39 AR-V7-negative patients.

8.2. *Justification of sample size*

The sample size is determined on the basis of the primary endpoint. The primary endpoint is defined as PFS according to the PCWG2 criteria. We will screen the AR-V7 mutation retrospectively, after the patient was included. We expect the number of AR-V7-positive patients will be 25% of total sample. Therefore, sample size has been estimated on AR-V7-positive cohort to ensure a minimum of 80% power in two cohort analysis. We hypothesized equally efficacy of radium-223 in AR-V7-negative and AR-V7-positive cohorts.

Previous studies in advanced refractory prostate cancer patients treated with docetaxel plus estramustine against mitoxantrone plus prednisone showed a median PFS of 6.3 and 3.2 months, respectively[26]. According to these results, excluding a PFS \leq 3 months while targeting an improvement of the PFS \geq 6.3 months would be a conservative approach to evaluation of the radium-223 effect in both cohorts. The analysis will be performed with one arm one-sided Log-Rank test. We program a 23 months of accrual period and 11 months of follow-up period (maximum follow-up of 34 months). We assume an uniform accrual of 2.26 patients per month (both cohorts). A sample size of 52 patients will be needed to attain 80% power at nominal level of one-sided alpha of 0.05. Therefore, we expect to include a total sample of 52 patients, 39 of them will be AR-V7-negative and 13 AR-V7-positive patients.

Safety follow-up extension of the study.

The maximum follow-up of the study for primary and secondary efficacy analysis will be 34 months. However we will include a 2-years extension after the end of the treatment (April 2019) to evaluate bone lesions. Additionally, analysis of overall survival will be also extended.

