#### **Methods for primary analysis**

The study will be declared positive if the median PFS of radium-223 in total sample is

EudraCT number: 2016-001888-36

statistically significantly better compared with null hypothesis (PFS  $\leq$  3 months;  $p < 0.05$ ).

The analysis will be based on the maximum-likelihood for exponential distribution test.

Additionally, the PFS will be analyzed with Kaplan Meier method in all patients and in both cohorts. We will provide the number and proportion of events and median survival time with corresponding 95% CI.

The primary analysis will be conducted on the full analysis set. The analysis in per protocol set will be considered as supportive.

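### The null median of 3.0 months is called conservative, but it lies below the 3.2-month comparator that the plan cites, so a positive result need not show PFS longer than that comparator

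*Protocol*

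**What the plan says.** Protocol 8.2, repeated in SAP 4.7, rests the hypotheses on one earlier randomised trial in advanced refractory prostate cancer. Docetaxel plus estramustine and mitoxantrone plus prednisone "showed a median PFS of 6.3 and 3.2 months, respectively". From these two figures the plan sets a null of PFS no longer than 3 months and a target of at least 6.3 months, and says that this choice "would be a conservative approach to evaluation of the radium-223 effect in both cohorts". It gives no reason for 3.0 in place of 3.2, and the documents contain no other figure for the null.

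The size follows from the same section: "sample size has been estimated on AR-V7-positive cohort to ensure a minimum of 80% power in two cohort analysis". With "We expect the number of AR-V7-positive patients will be 25% of total sample", this becomes 13 positive patients and 52 in total, and "A sample size of 52 patients will be needed to attain 80% power at nominal level of one-sided alpha of 0.05".

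The decision rule applies to the total sample. Protocol 8.3.6 and SAP 7.1.1 declare the study positive if median PFS is "statistically significantly better compared with null hypothesis" at p < 0.05, and SAP 7.1.1 repeats the null of 3 months. The protocol names a one-sample log-rank test; the SAP names a maximum-likelihood test for an exponential distribution.

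**The concern.** With no control arm, the null median is the entire comparison. The plan takes the better arm's median unchanged as its target but moves the worse arm's median down before using it as the null. Both consequences favour the trial. The bar for success is lower, and the assumed ratio of medians grows from 6.3/3.2 = 1.97 to 6.3/3.0 = 2.10, which shrinks the required sample. A reader told that the choice is conservative will assume the opposite.

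What is at stake is the meaning of a borderline positive result. Such a result could be reported as activity beyond historical experience while a median of 3.2 months, the only comparator value in the documents, has not been excluded.

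**Working it through.** **Inputs.** From protocol 8.2: null 3.0 months, target 6.3, cited comparator 3.2, one-sided 0.05, 80% power, 23 months of accrual, 11 months of follow-up, 25% AR-V7-positive, 52 patients. Assumed because the sample-size text is silent: exponential PFS, no dropout, exact event times.

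**1. Reproduce the plan's size.**
- Events needed = ((1.645 + 0.842) / ln(6.3/3.0))² = (2.487/0.742)² = 11.23.
- With uniform accrual over a = 23 and follow-up f = 11, P(event) = 1 − [exp(−λf) − exp(−λ(a+f))]/(λa), where λ = ln 2/median. At 6.3 months this is 0.892.
- 11.23/0.892 = 12.6, so 13 patients; 13/0.25 = 52. Power with 13 is 81% in closed form and about 80% by simulation (one-sample log-rank or exponential Wald).

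The stated design is reproduced, so the model matches the plan.

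**2. Chance of a positive trial if the true median is 3.2 and the null is 3.0.**
- P(event) at 3.2 months = 0.982, so 52 patients give about 51.0 events.
- P(positive) = Φ(√51.0 × ln(3.2/3.0) − 1.645) = Φ(0.461 − 1.645) = Φ(−1.184) = 11.8%.

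Simulated rejection rates for 52 patients, one-sided 0.05:

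| Test version | True 3.0, null 3.0 | True 3.2, null 3.0 |
|---|---|---|
| One-sample log-rank, expected-events variance | 4.0% | 10.4% |
| Exponential Wald (log hazard) | 3.9% | 10.4% |
| Exponential chi-square | 5.0% | 12.4% |
| One-sample log-rank, observed-events variance | 5.7% | 13.9% |

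At one-sided 0.025 the closed form gives Φ(0.461 − 1.960) = 6.7%, and simulation gives about 5.5% to 8.9%. This case is included because protocol 8.3 makes tests two-sided by default, and the decision rule gives only p < 0.05.

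The excess depends on the sample size. In 13 patients alone the closed form gives 7.9% at one-sided 0.05.

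**3. What a test against 3.2 would require.**
- With about 51 events, the estimated exponential median must reach about 3.0 × exp(1.645/√51) = 3.78 months to beat 3.0, and 3.2 × exp(1.645/√51) = 4.03 months to beat 3.2. A result between these passes the plan's rule without excluding 3.2.
- Total-sample power at 6.3 months against 3.2: Φ(√(52 × 0.892) × ln(6.3/3.2) − 1.645) = Φ(4.61 − 1.645) = 99.8%.
- With 13 AR-V7-positive patients: Φ(√(13 × 0.892) × 0.677 − 1.645) = 74.6% in closed form, and about 73-74% by simulation with the log-rank (expected-events variance) or Wald test.
- Events for 80% power against 3.2: (2.487/0.677)² = 13.5; 13.5/0.892 = 15.1, so 16 positive patients, or 64 in total.

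**The case against.** The strongest reply is that the plan's null is 3.0 and the test holds its level there. Rejecting at a true 3.2 is then a correct rejection, not a false positive. This stands. A reader might infer that the type I error is doubled; the documents do not support that, because the excess exists only if 3.2 is taken as the level of an inactive treatment. Nor does the plan name 3.2 as its historical control. It is one arm's median in a trial of another population, and choosing a null from a loosely matched benchmark is a matter of judgement. That does not rescue the word conservative: the plan derives its hypotheses from these results, and if they do not fit, 3.0 has no support either.

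Second, the gap of 0.2 months (about 6 days) is small beside a scan interval of 12 weeks (2.76 months). This also stands, and it limits the figures. If medians refer to true event times, dating progression at the next scan lengthens recorded PFS. As an illustration, with half of all progressions dated that way (an assumption), the test rejects about a quarter of the time even when true and null medians are both 3.2. If the earlier trial's medians were scan-dated too, comparability turns on its schedule and PFS definition, which the documents do not give.

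Third, the Kaplan-Meier median with its 95% CI is planned, so readers could see for themselves whether 3.2 is excluded. That helps, but it does not tie the trial's claim to it.

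**Conclusion.** For the null, the conservative label is wrong: a value below the cited comparator is anti-conservative, and no reason is given for it. If the true median is 3.2 months, the total-sample rule declares success about 10-14% of the time at one-sided 0.05, or about 5-9% at one-sided 0.025. Both ranges assume exponential PFS, exact event times and no dropout, and neither covers the effect of 12-weekly scans.

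Two stronger conclusions are tempting and do not follow. The sample size is not miscalculated: 13 and 52 are reproduced from the stated inputs. And the primary null need not be replaced. SAP 7.6 records an unplanned interim analysis for a congress abstract, so changing the primary hypothesis now would come after data had been seen, and it would also break the stated minimum of 80% power in the AR-V7-positive cohort. A result near 6.3 months is unaffected. The point matters for a modest positive result.

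**What to change.** - **Protocol 8.2 and SAP 4.7:** delete the word conservative.
- **SAP 7.1.1:** keep 3.0 months as the primary null. Add a one-sided test of the total sample against 3.2 months, using the same statistic as the primary test. State that a result positive only against 3.0 does not show PFS longer than the cited comparator.
- **Power statement:** give the added test's power at 6.3 months as about 99.8% in the total sample, and about 73-74% in 13 AR-V7-positive patients with the one-sample log-rank or exponential Wald test.

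With the same statistic and level, passing against 3.2 implies passing against 3.0, so the added test needs no alpha adjustment. The cost is one extra analysis and a more limited claim if the result is borderline. No patients or procedures are added.

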8.3.6. Decision rules and adjustment of alpha for primary endpoint

The study will be declared positive if the median PFS of radium-223 in total sample is statistically significantly better compared with null hypothesis ($p < 0.05$).

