##### Justification of sample size

The sample size is determined on the basis of the primary endpoint. The primary endpoint is defined as PFS according to the PCWG2 criteria. We will screen the AR-V7 mutation retrospectively, after the patient was included. We expect the number of AR-V7-positive patients will be 25% of total sample. Therefore, sample size has been estimated on AR-V7-positive cohort to ensure a minimum of 80% power in two cohort analysis. We hypothesized equally efficacy of radium-223 in AR-V7-negative and AR-V7-positive cohorts.

Previous studies in advanced refractory prostate cancer patients treated with docetaxel plus estramustine against mitoxantrone plus prednisone showed a median PFS of 6.3 and 3.2 months, respectively. According to these results, excluding a PFS  $\leq 3$  months while targeting an improvement of the PFS  $\geq 6.3$  months would be a conservative approach to evaluation of the radium-223 effect in both cohorts. The analysis will be performed with one arm one-sided Log-Rank test.

A maximum follow-up period of 34 months is planned. We assume an uniform accrual of 2.26 patients per month (both cohorts). A sample size of 52 patients will be needed to attain 80%

EudraCT number: 2016-001888-36

power at nominal level of one-sided alpha of 0.05. Therefore, we expect to include a total sample of 52 patients, 39 of them will be AR-V7-negative and 13 AR-V7-positive patients. Safety follow-up extension of the study.

The maximum follow-up of the study for primary and secondary efficacy analysis will be 34 months. However, we will include a 2-years extension after the end of the treatment (April 2019) to evaluate bone lesions. Additionally, analysis of overall survival will be also extended.

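### The 80% power stated for 52 patients belongs to a test in 13 AR-V7-positive patients; the total-sample test that decides the trial has power above 99%, which neither document states

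*Protocol*

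**What the plan says.** Protocol 8.2 sizes the trial against a null median PFS of 3 months and a target of 6.3 months, using a one-sample, one-sided log-rank test with 23 months of accrual and 11 months of follow-up. It gives the basis for the size: "Therefore, sample size has been estimated on AR-V7-positive cohort to ensure a minimum of 80% power in two cohort analysis". It adds "We expect the number of AR-V7-positive patients will be 25% of total sample" and "We hypothesized equally efficacy of radium-223 in AR-V7-negative and AR-V7-positive cohorts", and Protocol 8.1 gives the split: "We expect to include 13 AR-V7-positive and 39 AR-V7-negative patients". The summary sentence then attaches the power to the whole trial: "A sample size of 52 patients will be needed to attain 80% power at nominal level of one-sided alpha of 0.05". SAP 4.7 carries the same reasoning and the same sentence, beginning "A sample size of 52 patients will be needed to attain 80".

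The rule for success concerns a different population. Protocol 8.3.6 says: "The study will be declared positive if the median PFS of radium-223 in total sample is statistically significantly better compared with null hypothesis". SAP 7.1.1 repeats that rule with the 3-month null.

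The two documents plan different tests. Under the primary endpoint, Protocol 8.4 plans one-sample log-rank tests in both cohorts. SAP 7.1.1 plans an exponential maximum-likelihood test for the primary analysis, and describes PFS by Kaplan-Meier in all patients and in each cohort.

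**The concern.** A reader who puts the summary sentence beside the decision rule will conclude that the test declaring success has 80% power at 6.3 months. In a single-arm trial the stated power is one of the few guides to how demanding the success criterion is. If the deciding test is far more powerful than stated, it will usually be met by a true median well below the 6.3-month target, and a positive result would show that 3 months was exceeded without saying much about 6.3 months. Meanwhile the test that the 80% does describe lies outside the decision rule, and the SAP does not carry it out.

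**Working it through.** **Inputs.** From Protocol 8.2: null median 3 months, target 6.3 months, uniform accrual over 23 months, 11 months of follow-up, one-sided alpha 0.05 (z = 1.645), 25% AR-V7-positive, 52 patients in total. The documents give no PFS distribution, dropout rate or allowance for scan timing in the sizing. I assume exponential PFS, no dropout, and progression dated when it occurs.

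**Step 1: event probability at 6.3 months.** With λ = ln 2/6.3 = 0.1100,

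P(event) = 1 − [exp(−11λ) − exp(−34λ)]/(23λ) = 1 − (0.2981 − 0.0237)/2.5305 = 0.892.

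**Step 2: reproduce the plan's figure.** With d expected events, power ≈ Φ(√d × ln(6.3/3) − 1.645), and ln(6.3/3) = 0.742.

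- n = 13: d = 13 × 0.892 = 11.6; power = Φ(3.404 × 0.742 − 1.645) = Φ(0.881) = 81.1%.
- n = 12: 78.3%, so 13 is the smallest number reaching 80% by this formula. Other standard approximations put it between 10 and 16.
- 13/0.25 = 52, and the accrual agrees: 2.26 × 23 = 51.98.

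The plan's 52 and 80% therefore reproduce as the AR-V7-positive cohort's figures.

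**Step 3: the test in the decision rule.** n = 52: d = 52 × 0.892 = 46.4; power = Φ(6.809 × 0.742 − 1.645) = Φ(3.407) = 99.97%. Across all the analytic forms tried, the lowest one-sided value is 99.7% and the lowest two-sided value is 99.4%. None gives 80% with 52 patients tested.

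**Step 4: where the total-sample rule has 80% power.** At a true median of 4.3 months the event probability is 0.955, so d = 49.7 and power = Φ(7.048 × 0.360 − 1.645) = Φ(0.892) = 81.4%. At 4.2 months it is 76.7%. With about 50 events, the smallest significant estimate of the median is 3 × exp(1.645/√50) ≈ 3.8 months.

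**Step 5: simulation** (200,000 trials per setting; ranges cover log-rank and exponential likelihood forms of the test).

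| Sample | True median (months) | One-sided 0.05 | Two-sided 0.05 |
|---|---|---|---|
| 13 | 6.3 | 80.0% to 84.8% | 70.1% to 77.9% |
| 52 | 6.3 | 99.95% to 99.97% | 99.88% to 99.92% |
| 52 | 3 (null) | 4.1% to 5.1% | 1.8% to 2.5% |

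A separate simulation of the one-sided log-rank test with n = 52 gives about 80% power at 4.3 months and about 97% at 5 months. In the null row, the two-sided column counts only rejections in favour of radium-223.

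**Step 6: will there be 13 positives?** AR-V7 status is determined after inclusion. If the number positive is binomial (52, 0.25), the chance of 12 or fewer is about 45%.

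**The case against.** The strongest reply is that the plan already discloses where 80% comes from. A few lines before the summary sentence, both documents say that the size was set on the AR-V7-positive cohort for a minimum of 80%. Power above 99% in the total sample satisfies a minimum, and sizing on the smallest planned analysis is legitimate when Protocol 8.4 plans cohort tests. All of this stands. A reader might infer a calculation error, but 13/0.25 = 52 reproduces the plan exactly.

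A reader might also infer that the rule is too easy in the sense of giving false positives. The documents do not support that. The declared aim is to exclude a median of 3 months or less, so success at a true 4.3 months is a correct rejection. Under the assumptions above, the simulated one-sided rejection rate at 3 months stays near or below 5%.

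The 4.3-month figure is conditional. Protocol 8.3 makes tests two-sided unless stated otherwise, and Protocol 8.3.6 and SAP 7.1.1 give only p < 0.05. The one-sided reading rests on the sizing text; a two-sided test would move the 80% point to about 4.5 months. Scans are 12-weekly. If every event were dated to the next scan, simulated success at a true 4.3 months would be about 99.9%, because recorded times would run later than true times. That is an extreme case, since deaths and skeletal events carry their own dates.

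The disclosure does not settle two things. Neither document gives the power of the deciding test, and the SAP drops the cohort test that the 80% describes.

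**Conclusion.** The concern holds as a mismatch between the stated power and the deciding test. The 80% describes a one-sample, one-sided 0.05 test in 13 AR-V7-positive patients. The total-sample rule has power above 99% at 6.3 months and reaches 80% at about 4.3 months, given exponential PFS, no dropout, a one-sided 0.05 test and continuously observed progression. The statement that it exceeds 99% at 6.3 months is unchanged by sidedness or the form of the test. The 4.3-month figure depends on sidedness and on how progression is dated, and should not be quoted without those conditions. More decimal places than "above 99%" would depend on the formula chosen.

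The AR-V7-positive figure is itself conditional on 13 positives. Fewer are expected about 45% of the time at 25% prevalence. SAP 8.5 counts unknown status as negative, and SAP 7.2.1 and 7.2.2 fall back to description if very few positives are recruited. The mismatch does not change the sample size or the decision rule. It changes what a reader may conclude from a positive result.

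**What to change.** In Protocol 8.2 and SAP 4.7:

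- Assign the 80% power at 6.3 months to the one-sample, one-sided 0.05 test in AR-V7-positive patients, conditional on 13 being found, and note the roughly 45% chance of fewer at 25% prevalence.
- State that the total-sample rule has power above 99% at 6.3 months and 80% at a true median of about 4.3 months. Give the assumptions beside those figures: one-sided 0.05, exponential PFS, no dropout, continuously observed progression. Note that 12-weekly scans would change the 4.3-month figure.

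Then reconcile Protocol 8.4 (one-sample log-rank in both cohorts) with SAP 7.1.1 (exponential test in the total sample, cohorts by Kaplan-Meier only), so that every stated power refers to a test that will be run. State the sidedness of the deciding test in Protocol 8.3.6 and SAP 7.1.1.

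The cost is wording in the two documents. No patients are added and the decision rule's population is unchanged. If the cohort test is kept, the SAP gains one short analysis.

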8.3. Statistical plan

Unless otherwise mentioned all tests will be two-sided.

8.3.1. Primary efficacy endpoint

The primary efficacy endpoint is the median PFS achieved with radium-223 treatment. The PFS will be evaluated at the first 34 months period of the study. The PFS will not be evaluated at the 2-years extension of the study for safety. PFS is a composite endpoint defined as the time from the start of the radium-223 treatment to disease progression in bone or soft-tissue, symptoms, or death, according to the modifiedPCWG2 criteria. Objective radiographic disease progression is defined as the presence of at least one of the following conditions:

- Bone lesion progression (appearance of \geq two new bone lesions compared to baseline).
- Soft-tissue lesion progression according to the RECIST criteria version 1.1.
- Presence of symptomatic skeletal events.

Patients with no progression will be censored at the date of their last evaluation. Censoring rules are specified in Table 2.

Table 2. Censoring rules for PFS

Situation	Date of progression or censoring	Outcome
Progression documented between scheduled visits	Earliest of: 
 
• Date of radiological assessment showing new lesion (if progression is based on new lesion); or 
• Date of last radiological assessment of measured lesions (if progression is based on increase in sum of measured lesions); or 
• Bone lesion progression (appearance of \geq two new bone lesions compared to baseline); or 
• Presence of symptomatic skeletal events (pathological fractures, spinal cord compression, radiation or surgery to bone) 	Progressed
Death before first progression disease assessment	Date of death	Progressed
Death between adequate assessment visits	Date of death	Progressed
No progression	Date of last radiological assessment of measured lesions	Censored
Treatment discontinuation for undocumented progression	Date of last radiological assessment of measured lesions	Censored
Treatment discontinuation for toxicity or other reason	Date of last radiological assessment of measured lesions	Censored
Death or progression after more than one missed visit	Date of last radiological assessment of measured lesions	Censored

